COVER PAGE

Title: Reducing Treatment Risk in Older Patients With Diabetes: Comparative Effectiveness of Academic Detailing With and Without Pre-Visit Patient Preparation

ClinicalTrials.Gov Registration: NCT04585191

12/2/2024 (revised 3/6/2025)

RETRO RCT Analytic Plan

Background

Over one-quarter of people aged 65 and older have type 2 diabetes, and this proportion is expected to increase rapidly in coming decades. Glycemic control in older patients must balance the short-term risks of treatment (e.g., hypoglycemia and its immediate consequences) with the long-term benefits of reduced microvascular complications (e.g., diabetic retinopathy or renal disease). Of increasing concern, hypoglycemia has become the leading preventable complication of treatment in this older population and increases the risk of cognitive decline, falls, lower health-related quality of life, hospitalization, and death. These severe consequences of hypoglycemia begin to change the balance between treatment benefit and risk as patients get older and develop increasing frailty and additional co-morbid chronic conditions. As patients age, they are less likely to experience the long-delayed benefits associated with tight glycemic control and more likely to suffer from the short-term risk of treatment-related hypoglycemia. This changing balance creates a critically important decisional dilemma of how best to balance long-term treatment goals with short-term treatment risks to optimize current health and well-being.

Design and Methods

We will conduct a comparative effectiveness randomized clinical trial involving the following two strategies for changing clinical management, both of which are transportable to a wide range of clinical settings and can be readily adopted into clinical practice:

1. **Academic detailing** is a well-validated strategy for changing prescribing practices that employs focused and pragmatic education for practicing clinicians. Academic detailing sessions are generally brief (30-45 minutes), integrated into the usual workday (e.g. during practice weekly meetings or lunches), and consist of clearly presented summaries of current evidence and guideline recommendations.
2. **Patient pre-visit preparation** is a more patient-centric strategy that has shown efficacy for improving clinical interactions and shared decision making. In this strategy, patients are prepared for clinical encounters prior to visits. Information exchange is bi-directional (i.e., patients receive information about relevant trade-offs and provide information about preferences and other relevant information to facilitate collaborative decision making with their provider).

The study has the following aims and design:

Aim 1: To compare academic detailing alone (Arm 1) to academic detailing + patient pre-visit preparation (Arm 2). We will measure differences in medication de-prescribing rates among well-controlled older patients with type 2 diabetes at high risk for medication-related hypoglycemia. [primary clinical outcome]

Aim 2: To compare differences between these 2 arms in patient-reported diabetes distress, decisional confidence, and perceived quality of care. [primary patient-reported outcomes]

Protocol Summary

Importance: Medication-related hypoglycemia is the leading cause of iatrogenic complications among older adults with type 2 diabetes (T2D).

Objective: Compare two strategies for insulin and/or sulfonylureas deprescribing in older patients with T2D treated in a PCP-randomized clinical trial (RCT).

Interventions: PCPs will 1+ academic detailing (AD) sessions that provide evidence to support diabetes medication reassessment and potential deprescribing strategies in older patients with T2D. Prior to their visit with a participating PCP, trial patients will be randomly assigned to receive either a pre-visit deprescribing activation handout or an attention control healthy lifestyle handout.

Main Outcomes and Measures: Primary outcomes (assessed at 6 months) are diabetes medication deprescribing (an aggregate measure) and any patient-reported severe hypoglycemia episodes.

Protocol Details

1. **RCT Eligible Participants**

- a. Kaiser Permanente members aged 75+ years with Diabetes Type 2
- b. Inclusions:
 - i. Hemoglobin A1c<=8% (in-control)
 - ii. Current use (in prior six months) of insulin and/or sulfonylurea
 - iii. Consent to participate in the study
- c. Exclusions:
 - i. Deceased
 - ii. End of KP Membership
 - iii. Does not speak English
 - iv. Medical exclusions (Type 1 diabetes, cognitively impaired, palliative care, chemo regime)

2. **Study period**

- a. Patients provisionally enrolled from October 1, 2020-July 31, 2023
 - i. Patients provisionally enrolled based on verbal consent
 - ii. Enrollment and official consent are upon initial patient encounter with their PCP
- b. Follow-up from October 1, 2020-September 15, 2024
- c. Index Date (T0)
 - i. Initial Patient Encounter with their PCP (e.g., visit, secure message) following receipt of packet
- d. Follow-up Period – Analyze two time points
 - i. 6 months following the index date (T6)
 - 1. Follow-up survey may be more than six months after the initial visit, depending on when the RAs are able to successfully contact the patient for the follow-up survey
 - ii. 12 months following the index date (T12)

3. **Study Arms**

- a. Study Arm Assignment
 - i. PCPs were randomized upon Academic Detailing session attendance
 - ii. Patients were assigned to a study arm based on their PCP on file upon enrollment
- b. Arm 1 (Control): Academic Detailing + General Packet
- c. Arm 2 (Intervention): Academic Detailing + Patient Pre-Visit Preparation Packet

Statistical Analysis Plan (SAP)

We will construct generalized estimating equation (GEE) models to compare changes from baseline in clinical and patient-reported outcomes ($p < 0.05$) between clinical trial arms. All statistical analyses will use SAS 9.4 (SAS Institute Inc), and regression models were fit using PROC GENMOD. For each deprescribing, patient-reported and hypoglycemia-related outcome, we will construct a regression model with baseline measurements of the outcome included as covariates and a repeated statement to account for patient clustering within PCP panels. We will also examined heterogeneity of treatment effect (HTE) based on demographic and baseline clinical variables by calculating interaction term p-values from the models with and without interaction terms at 6 and 12 months for the deprescribing primary outcome.

The Table lists each baseline covariate that will be used in each outcome model.

Outcome Model	Baseline Covariate(s) Included
Any deprescribing (T6 and T12 models)	On insulin at T0 – y/n and on sulf at T0 – y/n
Self-reported severe hypoglycemia event from T6 patient survey	Self-reported severe hypoglycemia event from T0 patient survey
Hypoglycemia-related ED or IP diagnosis (T6 and T12 models)	Hypoglycemia-related ED or IP diagnosis in 1 year prior to T0
HbA1c lab result (T6 and T12 models)	Latest HbA1c lab result prior to T0 >8%

4. Outcomes

Outcome	Timepoints	Summary Statistic in Each Arm and At Each Timepoint	Effect Estimate, Difference in:	Initial Statistical Test
HbA1c Value	Baseline, Follow-up	Mean and CI	Means	T-test
HbA1c <=8	Baseline, Follow-up	% of Arm	Proportions	Chi-sq
Hypo IP	Baseline, Follow-up	% of Arm	Proportions	Chi-sq
Hypo ED	Baseline, Follow-up	% of Arm	Proportions	Chi-sq
ED	Baseline, Follow-up	% of Arm	Proportions	Chi-sq
IP	Baseline, Follow-up	% of Arm	Proportions	Chi-sq
PCP Visits	Baseline, Follow-up	% of Arm	Proportions	Chi-sq
Survey Responses	Baseline, Follow-up	% of Arm	Proportions	Chi-sq
PEPPI Scores	Baseline, Follow-up	Mean and CI	Means	T-test
PAID5 Scores	Baseline, Follow-up	Mean and CI	Means	T-test
RAND PSQ	Follow-up	% of Arm	Proportions	Chi-sq

a. Primary Outcomes

- i. Deprescribing of either insulin or SU
 - 1. Discontinuation of either insulin or SU
 - 2. Reduction in dose of insulin or SU
 - 3. Switch from a higher risk to lower risk version of insulin
- ii. Timeframe for determining baseline and follow-up medication regimen
 - 1. Single-date regimen at T0, T6, and T12

b. Secondary Outcomes

- i. Changes in HbA1c levels
 - 1. Baseline HbA1c: Use most recent prior to T0 in the year prior to T0; if no HbA1c in year prior to T0, pull forward eligibility HbA1c
 - 2. Follow-up T6: in this timeframe, pick the HbA1c closest to T6
 - 3. Follow-up T12: in this timeframe, pick the HbA1c closest to T12?
- ii. Hypoglycemic-related hospitalizations
- iii. Hypoglycemic-related ED visits
 - 1. Number of hypoglycemic-related ED visits between T0-T6

c. Patient-reported outcomes (Change between baseline and follow-up questionnaires)

- i. Incidence of patient-reported moderate and severe hypoglycemic events
- ii. Less diabetes-related stress
- iii. Perceived quality of care

5. **Baseline data**

- a. PCP Data
- b. Patient Data
 - i. Demographics: Race, Ethnicity, Age, Gender, Language
 - ii. Patient Engagement: Kp.org status, Kp.org usage
 - iii. Comorbidities Data lookback: 1 year before study visit date
 - iv. Clinical Characteristics
 - 1. Medications: Diabetes Medication Regime (Insulin, Sulfonylurea), Medication Count (All Medications)
 - 2. Labs: HbA1c
 - a. Data lookback: 1 year before study visit date
 - b. HbA1c Selection: most recent one prior to T0
 - 3. Hypoglycemic-related hospitalizations
 - 4. Hypoglycemic-related ED Visits
 - v. Membership/Insurance
 - vi. Baseline Survey Responses

6. **Lost to Follow-up**

- a. Reasons
 - i. Loss of membership during study period
 - ii. Death
 - iii. PCP Switches

7. **Analyses**

- a. Comparison of baseline characteristics between intervention and control
- b. Comparison of consented vs declined
 - i. Characteristics as of Eligibility Date:
 - 1. Demographics: gender, age, race, ethnicity, language
 - 2. Study eligibility data: HbA1c, INS/SU Y/N
- c. Flow through the study
 - i. Time from provisional enrollment to actual enrollment
 - ii. Reasons for drop out and missing data
- d. Comparison of outcomes between intervention and control
 - i. Analysis of subsets of patients based on specific characteristics

8. **Final Analytic Tables**

- a. Enrolled vs Declined
- b. Table 1-Intervention vs Control
- c. PCP Table
- d. Outcomes table

9. **Sensitivity Analysis**

- a. Sensitivity analyses to assess the impact of missing data
- b. Sensitivity analyses based on modality of visit (virtual vs. in-person)
- c. Strata of people who had prior hypoglycemic events

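### Deprescribing at 6 months is primary throughout, but the plan contradicts itself on which other outcomes are primary and gives no rule for testing them

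*Combined protocol and SAP*

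**What the plan says.** Three places assign primary status, and they differ.

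- **Aims.** Aim 1 says "We will measure differences in medication de-prescribing rates among well-controlled older patients with type 2 diabetes" and tags this as the primary clinical outcome. Aim 2 compares the arms on "patient-reported diabetes distress, decisional confidence, and perceived quality of care. [primary patient-reported outcomes".
- **Protocol Summary, Main Outcomes and Measures.** "Primary outcomes (assessed at 6 months) are diabetes medication deprescribing (an aggregate measure) and any patient-reported severe hypoglycemia episodes".
- **Section 4.a, the only list headed as primary.** It has one entry, "Deprescribing of either insulin or SU", with the regimen read at T0, T6 and T12.

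Section 4.c holds patient-reported outcomes ("Change between baseline and follow-up questionnaires"). It lists "Incidence of patient-reported moderate and severe hypoglycemic events", then diabetes-related stress and quality of care. It calls none of them primary or secondary, and it does not name decisional confidence.

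The SAP text says: "For each deprescribing, patient-reported and hypoglycemia-related outcome, we will construct a regression model". One threshold, p < 0.05, covers clinical and patient-reported outcomes alike. The sentence on heterogeneity of treatment effect calls only deprescribing the primary outcome.

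**The concern.** A significant difference in severe hypoglycemia is a primary success under the Protocol Summary but not under the Aims or Section 4.a. A significant difference in distress, decisional confidence or quality of care is a primary success under Aim 2 but not under the Summary or Section 4.a. A null result on any of the four can be set aside in the same way, by citing a different part of the document.

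The plan has no ordering of tests, no alpha split, no adjustment and no statement that all primaries must succeed. For everything beyond deprescribing at 6 months, a reader therefore cannot tell which results are confirmatory or what error rate goes with them.

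**Working it through.** **Step 1. Set the lists side by side.**

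| Outcome | Aims | Protocol Summary | Section 4.a to 4.c | SAP text and covariate table |
|---|---|---|---|---|
| Deprescribing | primary | primary, 6 months | primary (4.a) | called primary; models at T6 and T12 |
| Patient-reported severe hypoglycemia | absent | primary, 6 months | 4.c, unranked, alongside moderate events | model row at T6 |
| Diabetes distress | primary | absent | 4.c, unranked (as stress) | no row |
| Decisional confidence | primary | absent | not named | no row |
| Quality of care | primary | absent | 4.c, unranked | no row |

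Only the first row agrees across columns. The Summary is the only place that ties primary status to a time point, and it says 6 months. T12 deprescribing is modelled but has no stated rank.

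**Step 2. See whether the tables settle it.** The covariate table has a row for severe hypoglycemia and none for the Aim 2 outcomes. That fits the Summary better than the Aims, but it is not decisive for two reasons. The table also carries HbA1c and hypoglycemia-related hospital and ED outcomes, which Section 4.b ranks as secondary, so a row does not imply primary status. The SAP text also promises a model for every patient-reported outcome. The outcomes table in Section 4 has rows for survey responses, PEPPI, PAID5 and RAND PSQ, so patient-reported analyses are planned, but that table ranks nothing.

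**Step 3. Size, if any one success counts.** The documents give no familywise error rate to reproduce. The only input is the 0.05 threshold, taken here as two-sided because sidedness is not stated. For k independent tests, the chance of at least one false positive is 1 − 0.95^k; whatever the dependence, it cannot exceed k × 0.05.

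- Section 4.a at T6, k = 1: 1 − 0.95 = 5%.
- Protocol Summary, k = 2: 1 − 0.9025 = 9.75% (bound 10%).
- Aim 2 alone, k = 3: 1 − 0.8574 = 14.3% (bound 15%).

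Positive correlation lowers these. For the Summary's two tests, treated as two-sided normal tests, an assumed correlation of 0.5 gives 9.1% and 0.9 gives 7.0%.

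If deprescribing at T6 and T12 were both counted as primary, k would again be 2, with 9.75% under independence. The two share patients, so the figure would probably be lower.

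**Step 4. Size, if all must succeed.** Error is not inflated, but power falls. With an assumed 80% power per test and independence, joint power is 0.80² = 64% for the Summary's pair and 0.80³ = 51% for Aim 2's three. The plan states neither rule.

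**The case against.** The strongest reply is that the main claim is not in doubt. Deprescribing is primary in Aim 1, the Summary, Section 4.a and the SAP's heterogeneity sentence, and 6 months is the one primary time point given. That stands. A reader might infer that the trial's main claim has no defined error rate. The documents do not support this, because deprescribing at T6 taken as a single test has a nominal 5%.

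A second reply is that the Aims use two labels, one clinical and one patient-reported, each tied to its own aim, and separately labelled domains need not share one error budget. That also has force. Pooling both Aims into four tests (1 − 0.95⁴ = 18.5%), or taking all five outcomes called primary anywhere (1 − 0.95⁵ = 22.6%), builds a family that no section states. Both figures are hypothetical.

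A third reply is that Sections 4.a and 4.c simply mirror the clinical and patient-reported split of the Aims. They may, but 4.c does not say so, adds hypoglycemia, and leaves out decisional confidence. This reading also does not explain the Summary's list.

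A reader might also infer from the dates that outcomes were picked after results were seen. The plan is dated 12/2/2024 and revised 3/6/2025, follow-up ended September 15, 2024, and one clause reads "regression models were fit using PROC GENMOD". The same paragraph mixes tenses, so this may be a drafting slip, and nothing in the documents shows that results drove the choice. This is a side note, not a defect.

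**Conclusion.** The concern holds for the outcomes other than deprescribing at 6 months. The Aims, Protocol Summary and Section 4 give incompatible answers on whether severe hypoglycemia and the three Aim 2 outcomes are primary. T12 deprescribing has no rank, and no testing rule covers any of these. This is a conflict between stated rules rather than missing detail, and it must be fixed before any of these results is described as primary or confirmatory.

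The figures of 9.75% for the Summary's pair and 14.3% for Aim 2's three rest on three assumptions: any single success supports a claim, the tests are independent, and each is two-sided at 0.05. They describe how far the two lists could inflate error. They are not an error rate that the plan has adopted.

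**What to change.** Use one primary list, identical in the Aims, the Protocol Summary and Section 4.

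1. If a primary list and testing rule dated before access to outcome data exist, adopt them and cite the date.
2. If they do not, say so, and do not call any newly chosen list or test order prespecified, deprescribing included. Then use a single default:
   - Deprescribing at T6 is the sole first test, at two-sided 0.05.
   - Patient-reported severe hypoglycemia at T6 is tested at 0.05 only if deprescribing is significant.
   - T12 deprescribing and the Aim 2 outcomes are labelled secondary and reported with confidence intervals and no confirmatory claim. Aim 2's label is changed to match.

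Under this default the two confirmatory tests together hold the familywise error at 5%, and deprescribing keeps its full 0.05.

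The work is a search for earlier dated versions and some rewording; no new data are needed. The price is fewer confirmatory results, and severe hypoglycemia can be claimed only after deprescribing succeeds. As illustration, with an assumed 80% power for each test and independence, the chance of claiming severe hypoglycemia falls from 80% to 0.80 × 0.80 = 64%. The actual loss cannot be worked out, because the documents give no sample size or event rates.

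### No small-sample method is named for the PCP-clustered GEE tests; under GENMOD's default, a 5% test of a common outcome can run at roughly 7–13% if only 16–40 PCPs contribute

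*Combined protocol and SAP*

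**What the plan says.** Under Study Arms, "PCPs were randomized upon Academic Detailing session attendance", and "Patients were assigned to a study arm based on their PCP on file upon enrollment". The arm is therefore constant within a PCP's panel.

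The Statistical Analysis Plan section begins "We will construct generalized estimating equation (GEE) models", whose purpose is to "compare changes from baseline in clinical and patient-reported outcomes ($p < 0.05$) between clinical trial arms". It adds that "regression models were fit using PROC GENMOD" in SAS 9.4, and that each outcome model has the baseline value as a covariate and "a repeated statement to account for patient clustering within PCP panels". The deprescribing model carries two binary covariates, insulin use and sulfonylurea use at T0.

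The plan does not give the working correlation, whether standard errors are empirical or model-based, whether tests are Wald or score, the reference distribution, or any finite-sample correction. It gives no number of PCPs, patients per PCP, ICC or expected event rate. The Sensitivity Analysis section covers missing data, visit modality and prior hypoglycemia, but not the number of clusters.

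**The concern.** When the arm is set at PCP level, the information on the arm effect is governed largely by how many PCPs contribute, not only by how many patients. GENMOD's repeated statement reports, by default, an empirical (sandwich) standard error with a z-test. That standard error is biased downward when clusters are few, and the normal reference ignores the limited degrees of freedom. Both push a common-outcome test above its nominal level and make the confidence interval too narrow.

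The T6 deprescribing comparison is most exposed, because it is a primary outcome and is plausibly common. Subset analyses and the stratum with prior hypoglycemic events may draw on fewer PCPs than the main analysis.

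**Working it through.** **Inputs.** From the documents: PCP randomisation, GEE in GENMOD with PCP panels as clusters, threshold 0.05 (two-sided assumed). Assumed, because not given: number of PCPs (K), panel sizes, ICC, event rate. The plan states no figure that could be reproduced.

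**Step 1: closed form.** Take K equal panels split 1:1 with normal panel means. The uncorrected robust variance divides each arm's sum of squares by K/2 instead of K/2 − 1, so

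- SE ratio = √((K − 2)/K)
- true size = 2 × [1 − T(1.96 × √((K − 2)/K))], where T is the t distribution function on K − 2 degrees of freedom.

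For K = 40: √(38/40) = 0.975; 1.96 × 0.975 = 1.91; on 38 degrees of freedom the two-sided tail is 6.4%. For K = 16: √(14/16) = 0.935; 1.96 × 0.935 = 1.83; on 14 degrees of freedom the tail is 8.8%.

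**Step 2: simulation under the null.** Logistic GEE, arm set at PCP level, unequal panels, uncorrected sandwich with a z-test. Rejection rates in per cent:

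| PCPs | Closed form | A: mean 5 per PCP | B: mean 10, CV 1.0 | C: mean 2.5, CV 0.8 | D: mean 2.5–10, geometric |
|---|---|---|---|---|---|
| 10 | 11.8 | 11.0–11.5 | 18–20 | 6.4–6.5 | – |
| 16 | 8.8 | 9.4–9.7 | – | – | 9–13 |
| 20 | 7.9 | 8.7–9.5 | 12–12.5 | 5.6–6.6 | – |
| 24 | – | – | – | – | 7–11 |
| 40 | 6.4 | 6.1–6.8 | 8.2–8.3 | 5.8–6.2 | 7–9 |
| 60 | 5.9 | 5.5–6.2 | 7.2–7.5 | 6.1–6.3 | 6–7 |
| 100 | 5.5 | 5.3–6.3 | 6.1 | 4.8–5.5 | 5–8 |
| 200 | 5.3 | 5.0–5.2 | 5.3–5.5 | 5.2–5.9 | – |

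A, B and C use 20% events and one binary covariate; ICC is 0.02–0.05 in A and 0.05 in B and C. They have 3,000–4,000 runs per cell (Monte Carlo SE about √(0.05 × 0.95/3000) = 0.4 points at 5%). D uses 25% events and ICC 0.05. Only D exceeds 6.3% at 100 PCPs, and with panel means limited to 3–8 the same setting gave 5–6% there. So 5–6% is the central reading at 100, and 8% the highest value seen.

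**Step 3: panel size.** A smaller run of setting D with two covariates (up to 1,000 trials per cell) gave 5.6%, 10.3% and 13.0% at 16 PCPs for means of 2.5, 5 and 10 patients, and 7.2%, 8.4% and 10.6% at 24. Inflation rises with panel size. The 9% lower end for 16 PCPs is thus not a floor when panels are very small.

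**Step 4: rare outcomes.** With 5% events and a mean of 5 patients, one set gave 1.7–3.8% at 10–40 PCPs and about 5% from 60. Another gave about 4–6% at mean 5 and 8–9% at mean 10. Many runs were unusable, so only the lack of a uniform direction should be taken from this.

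**Step 5: alternatives, common outcome.**

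- Kauermann-Carroll sandwich with t on K − 4 (four parameters: intercept, arm, insulin, sulfonylurea): 4.0–6.6% at 16 PCPs and 4.7–6.1% at 24–100 for panel means 3–8; 2–7% over means 2.5–10. The small run in Step 3 gave 1.9% (mean 2.5) and 8.5% (mean 10) at 16 PCPs.
- Generalized score test: 2.2–5.9% in A–C and 3.7–6.7% in D.
- Sandwich rescaled by √(K/(K − 2)) with t on K − 2: 5.4–6.2% at 20 PCPs in A, but 8.3–8.9% in B.
- Mancl-DeRouen sandwich with t on K − 4: 1.5–5.5%, conservative at 16–24 PCPs.

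**The case against.** The strongest objection is that none of this is shown for this trial. The standard error and z reference are read from a software default, not from the plan, and GENMOD can also report model-based standard errors and score tests. Nothing in the documents says that PCPs are few; with 100 or more, the default and corrected tests are hard to tell apart. This stands, and it limits the point to a conditional one.

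A reader might infer that every modelled p-value is inflated. The documents do not support that. The heterogeneity p-values come from "calculating interaction term p-values from the models with and without interaction terms at 6 and 12 months", a model comparison that need not be a robust Wald z-test, and rare outcomes such as hypoglycemia-related admissions may behave differently. A reader might also expect small panels to be the worst case; the simulations point the other way.

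The Protocol Summary also says that "trial patients will be randomly assigned to receive either a pre-visit deprescribing activation handout or an attention control healthy lifestyle handout". If allocation were by patient, the arm would vary within panels and this argument would not apply as set out. But the same summary calls the trial PCP-randomised and the Study Arms section is explicit, so PCP randomisation is the better-supported reading. The sentence should be reconciled with it.

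Finally, no single correction is the only acceptable one. The score test needs no change of procedure, and the Kauermann-Carroll test is itself imperfect at 16 PCPs.

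**Conclusion.** The point holds as a conditional weakness. The plan randomises PCPs, names a procedure whose default test is anti-conservative with few clusters, and states neither a correction nor the cluster count. Under the default, and assuming 25% events, ICC 0.05 and unequal panels, a nominal 5% test of T6 deprescribing would run at roughly 7–13% with 16–40 PCPs, 6–7% with 60, and about 5–6% with 100–200. Very small panels would bring it lower; larger and more uneven panels, higher.

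It would go too far to say that the trial's tests are in fact inflated, since the number of contributing PCPs is unknown and the effect may be negligible. The case for acting is that the remedy is cheap and that the count should be available: follow-up closed on September 15, 2024, before the plan's dates of 12/2/2024 and 3/6/2025, and a PCP table is already planned.

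**What to change.** Add one paragraph to the SAP stating that arm-effect tests and confidence intervals from the GEE models use a small-sample method, and name it. Two suitable options in SAS 9.4:

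- The Kauermann-Carroll bias-corrected sandwich with t on (contributing PCPs minus model parameters), through PROC GLIMMIX with EMPIRICAL=ROOT and PCP as the residual-level subject. State the degrees of freedom explicitly. This covers both tests and intervals.
- GENMOD's generalized score test. This keeps the named procedure but supplies p-values only, so the interval method must be stated separately.

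Count contributing PCPs separately for each subset or stratum. State the working correlation and the test used for the interaction comparisons. Report PCPs and patients per PCP by arm in the planned PCP table.

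The cost is the paragraph and, for the first option, a change of procedure. Intervals become slightly wider if PCPs are few and change negligibly if they are many.

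### The two models for the Protocol Summary's primary outcomes use very few baseline covariates, forgoing modest precision and some protection against measured imbalance

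*Combined protocol and SAP*

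**What the plan says.** The Protocol Summary names two primary outcomes: "Primary outcomes (assessed at 6 months) are diabetes medication deprescribing (an aggregate measure) and any patient-reported severe hypoglycemia episodes". Section 4.a lists only deprescribing as primary and places patient-reported hypoglycemia under 4.c, so the second outcome's status is not consistent within the document.

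The SAP specifies GEE models with "a repeated statement to account for patient clustering within PCP panels", and introduces its covariate table with "The Table lists each baseline covariate that will be used in each outcome model". I read the table as the complete adjustment set:

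- Any deprescribing, T6 and T12: "On insulin at T0 – y/n and on sulf at T0 – y/n".
- Self-reported severe hypoglycemia, T6: "Self-reported severe hypoglycemia event from T0 patient survey".

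Section 5 lists as baseline data age, comorbidities, medication count, hypoglycemia-related hospitalizations and ED visits, and HbA1c ("HbA1c Selection: most recent one prior to T0").

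On allocation, Section 3 says "PCPs were randomized upon Academic Detailing session attendance" and gives each patient the arm of the PCP on file at enrollment. Section 2 puts formal enrollment, consent and T0 at the first PCP encounter after the packet has arrived. The Protocol Summary instead describes patients being assigned at random to a handout. These two accounts must be reconciled; the imbalance argument below rests on Sections 2 and 3.

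**The concern.** The Background says hypoglycemia's harms can "change the balance between treatment benefit and risk as patients get older and develop increasing frailty and additional co-morbid chronic conditions". Age and clinical risk are therefore natural candidates to predict whether treatment is reduced, yet the deprescribing model contains neither age, HbA1c nor prior hypoglycemia. The severe-hypoglycemia model does adjust for the prior event but does not distinguish insulin users from sulfonylurea users.

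Two things are at stake. Adjusting for values that predict the outcome makes the arm comparison more precise. In addition, when clusters are randomized first and patients join later, patient characteristics may differ between arms by more than they would under individual randomization. The packet differs by arm and precedes T0, so who reaches T0 could differ too. Clustering by PCP panel corrects standard errors for correlation; it does nothing about such a difference. Section 7 plans a baseline comparison of the arms but gives no rule for acting on what it shows.

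**Working it through.** The documents give no sample size, event rate, effect size, number of PCPs or intracluster correlation, so there is no plan figure to reproduce. Every numerical input below is an assumption, used only to show scale. All calculations treat patients as independent.

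**1. Precision, deprescribing.** Assume 24% deprescribing and odds ratios from 0.85 to 0.60 per SD of HbA1c, 1.1 to 1.3 per SD of age, and 1.5 to 2.5 for prior hypoglycemia (yes against no). In a simulation of 1,000,000 patients the planned covariates explain R² = 0.002. With the three added, R² is 0.012, 0.039 and 0.072 for weak, middle and strong predictors. The equivalent gain in patients is (1 − R²planned)/(1 − R²added) − 1:

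- weak: 0.998/0.988 − 1 = 1.0%
- middle: 0.998/0.961 − 1 = 3.9%
- strong: 0.998/0.928 − 1 = 7.5%

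A hand check for HbA1c and age alone uses added R² ≈ p(1−p) × Σ(ln OR)², with p(1−p) = 0.24 × 0.76 = 0.1824. Weak: 0.1824 × (0.0264 + 0.0091) = 0.006. Strong: 0.1824 × (0.2609 + 0.0688) = 0.060. Prior hypoglycemia accounts for the remainder, so the simulated values are plausible.

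**2. Imbalance in HbA1c, deprescribing, no true arm effect.** Shift in log-odds = imbalance in SD × ln(OR per SD).

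- 0.1 × ln(0.85) = −0.016 (OR 0.98)
- 0.2 × ln(0.60) = −0.102 (OR 0.90)

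| Assumed deprescribing rate | Small case | Large case |
|---|---|---|
| 15% | −0.21 points | −1.26 points |
| 24% | −0.30 points | −1.81 points |
| 30% | −0.34 points | −2.10 points |

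**3. A binary omitted covariate, as a second route.** Bias in risk difference = imbalance × [p(X=1) − p(X=0)]. Assume control-arm prevalence 30%, risk 15% to 30% without the factor, odds ratio 1.5 to 3, and imbalance of 5 to 15 points. The shift is 0.3 to 3.9 points (OR 1.02 to 1.19).

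**4. Drug class and severe hypoglycemia.** Assume 45% on insulin in one arm and 40% or 35% in the other, with risk 10% to 12% on insulin and 4% to 5% on sulfonylurea.

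- Smallest: (0.45 − 0.40) × (10 − 5) = 0.25 points
- Largest: (0.45 − 0.35) × (12 − 4) = 0.80 points

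A wider set (40% on insulin, risk 3% to 5% off insulin, odds ratio 2 to 4, imbalance 5 to 15 points) gives 0.1 to 1.9 points. Both ranges ignore the baseline-event covariate already in the model, which would absorb part of the shift.

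**5. Effect on the test.** With a 25% event rate and two-sided 0.05, a systematic shift of 1, 2 or 4 points gives rejection rates of 5.3%, 6.2% and 10.0% at an assumed 100 patients per arm, and 5.9%, 8.7% and 20.5% at 300.

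**The case against.** The strongest defense is that the SAP follows a stated rule: each model includes the baseline measurement of its own outcome. Baseline regimen and baseline event fit that rule, and a short covariate list is a legitimate choice. This stands. A reader might infer that the omissions bias the primary comparison; they do not by themselves.

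A reader might also infer that arm imbalance is present, or that adjustment would remove it. Neither is supported. No passage shows recruitment differing by arm, and the documents do not say whether recruiters or patients knew the arm at verbal consent. An imbalance of 0.1 to 0.2 SD can be ordinary chance: its standard error under individual randomization is √(2/n), which is 0.14 SD at an assumed 100 per arm and 0.08 at 300, and chance imbalance is already reflected in the standard error. Adjustment acts only on measured covariates and cannot cure unmeasured selection.

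Eligibility restricts age to 75 and over and HbA1c to 8% or below, which may weaken both as predictors. This stands in part: the HbA1c outcome model's covariate is a flag for a latest pre-T0 value above 8%, so the plan itself expects some spread beyond the limit. Likewise, every patient takes insulin or a sulfonylurea, so the severe-hypoglycemia model omits drug class, not exposure as such.

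The planned heterogeneity tests, baseline comparison and prior-hypoglycemia strata could reveal imbalance, but none adds a covariate to either main model.

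Timing is the weightiest objection. The plan is dated 12/2/2024 and revised 3/6/2025, follow-up ended September 15, 2024, and one sentence speaks of model fitting in the past tense. Replacing a primary model after arm results are known would be worse than leaving it sparse.

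**Conclusion.** The point holds as a missed improvement, not as an error that invalidates either analysis. The text is clear about what each model contains and about what is collected and left unused. The precision forgone for deprescribing is modest, about 1% to 7.5% in equivalent patients, given a 24% event rate, the assumed odds ratios and no clustering. If measured imbalance did arise, the assumed cases shift the deprescribing difference by roughly 0.2 to 3.9 points and the severe-hypoglycemia difference by 0.1 to 1.9 points, the latter overstated because the baseline event is already adjusted for. With small imbalance or a weak predictor the effect is minor. It becomes material only with imbalances of about 10 points or more in a strong predictor, and the documents do not show whether that occurred.

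The imbalance argument depends on the Section 3 account of allocation. The precision argument holds under either account.

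**What to change.** In the covariate table, add to the any-deprescribing row the latest HbA1c before T0 (continuous), age (continuous) and hypoglycemia-related ED/IP diagnosis in the year before T0 (y/n). Keep both drug-class terms and report the current model alongside.

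Add baseline insulin y/n and sulfonylurea y/n to the severe-hypoglycemia row only if the event count, pooled over arms, supports the extra terms. Leave the hypoglycemia-related ED/IP model unchanged, since sparse cells are the same worry there.

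State the date of the change relative to access to outcome data by arm. If arm-level results have already been seen, keep the stated models as primary and report the adjusted models as a labelled supporting analysis. Reconcile the Protocol Summary's account of patient assignment with Section 3.

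No new data are needed: these are planned baseline items, and Section 4.b already falls back to the eligibility HbA1c when none exists in the prior year. The cost is a late-dated SAP change and a few more model terms.
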